Non-interventional Study Protocol

Document Number:	c09063488-07
BI Study Number:	1160.261
BI Investigational Product(s):	Dabigatran etexilate (Pradaxa [®])
Title:	Non-interventional study describing patients' perception on anticoagulant treatment and treatment convenience when treated with Pradaxa [®] or Vitamin K Antagonist for Stroke Prophylaxis in Atrial Fibrillation
Brief lay title	Patient Convenience Study
Protocol version identifier:	1.0
Date of last version of protocol:	25 Jan 2016
PASS:	No
EU PAS register number:	Study not registered
Active substance:	B01AE07 - Dabigatran etexilate.
Medicinal product:	Dabigatran etexilate
Product reference:	EU/1/08/442/001-019
Procedure number:	NA
Marketing authorisation holder(s):	Boehringer Ingelheim International GmbH [name]
Joint PASS:	No
Research question and objectives:	
Primary objective: Describe the atrial fibrillation patient's treatment perception by using the PACT-Q[®] (Perception on Anticoagulant Treatment Questionnaire).
 
Secondary objective: Characterization of patient population (including dosing of Pradaxa[®])

2. LIST OF ABBREVIATIONS

AE	Adverse Event
AESI	Adverse Event of Special interest
ADR	Adverse Drug Reaction
AF	Atrial Fibrillation
ANCOVA	Analysis of Covariance
BI	Boehringer Ingelheim
CA	Competent Authority
CHA ₂ DS ₂ - VASc score	Congestive heart failure, Hypertension, Age (≥ 75), Diabetes mellitus, Stroke/TIA, Vascular disease, Age 65-74, Sex category
CI	Confidence Interval
CML	Local Clinical Monitor
CRA	Clinical Research Associate
CRF	Case Report Form
CTP	Clinical Trial Protocol
DEDP	Drug Exposure During Pregnancy
DMP	Data Management Plan
DVT	Deep Venous Thrombosis
eCRF	Electronic Case Report Form
EC	Ethics Committee
ECG	Electrocardiogram
EDC	Electronic Data Capture
EMA	European Medicine Agency
EudraCT	European Clinical Trials Database
FDA	Food and Drug Administration
GCP	Good Clinical Practice
GEP	Good Epidemiological Practice
GPP	Good Pharmacoepidemiology Practice
GVP	Good Pharmacovigilance Practices
GPV CTC	Global Pharmacovigilance Clinical Trial Coordinator
HAS-BLED	Hypertension, Abnormal renal and liver function, Stroke (1 point), Bleeding history or predisposition, Labile INR, Elderly (>65 years), Drugs and Alcohol.
ICH	International Conference of Harmonisation
ICSR	Individual Case Safety Report
IEC	Independent Ethics Committee
INR	International Normalized Ratio
IRB	Institutional Review Board
ISF	Investigator Site File
MAH	Marketing Authorisation Holder Activities
n.a.	Not applicable / not available
NIS	Non-Interventional Study
NVAF	Non valvular atrial fibrillation
OPU	Operative Unit
OAC	Oral Anticoagulation
PACT-Q [®]	Perception of Anticoagulant Treatment Questionnaire

PE	Pulmonary Embolism
SAE	Serious Adverse Event
SDV	Source Data Verification
SEAP	Statistical and Epidemiological Analysis Plan
SEASK	South East Asia South Korea
SOP	Standard Operating Procedure
SPAF	Stroke Prophylaxis (or Prevention) in Atrial Fibrillation
TMF	Trial Master File
VKA	Vitamin K Antagonist

4. ABSTRACT

Name of company: Boehringer Ingelheim Name of finished medicinal product: Pradaxa [®] (Dabigatran etexilate), or Vitamin K Antagonist (VKA)			
Name of active ingredient: Dabigatran, or VKA			
Protocol date: 25 January 2016	Study number: 1160.261	Version/Revision: 1.0	Version/Revision date: n.a.
Title of study:	Non-interventional study describing patients' perception on anticoagulant treatment and treatment convenience when treated with Pradaxa [®] or Vitamin K Antagonist for Stroke Prophylaxis in Atrial Fibrillation.		
Rationale and background:	
Pradaxa[®] (Dabigatran etexilate) is a direct Thrombin inhibitor approved in Europe, USA and many other Asian countries worldwide for the prevention of stroke and systemic embolism in adult patients with non- valvular atrial fibrillation with one or more risk factors. There is a lack of data on how atrial fibrillation patients in Asia perceive Pradaxa[®] treatment in the context of anticoagulation management.
 
The decision in clinical practice to use Pradaxa[®] as the first novel anticoagulant or established vitamin K antagonists depends on many factors related to the patient and prescribing physician.
 
The aim of this non-interventional study is to describe patients' perception of anticoagulant treatment when using Pradaxa[®] to prevent stroke and systemic embolism while suffering from non-valvular atrial fibrillation (according to its approved indication at the approved dosages in respective countries) in comparison to using Vitamin K Antagonist (VKA).
		
Research question and objectives:	
Objective 1: How do patients perceive anticoagulation treatment with Pradaxa[®] for stroke prevention in non-valvular atrial fibrillation (NVAf) in comparison with VKA?
 
 • • What is treatment expectation of newly diagnosed NVAf patients before they start treatment with VKA or Pradaxa[®] • 
Objective 2: What are the characteristics of patients receiving anticoagulation treatment for stroke prevention regarding demographics, physician rated scores, kidney function, treatment (choice of treatment, dosing)?
		
Study design:	Non-interventional study of AF patients in Asia with a current VKA therapy and subsequent initiation of Pradaxa [®] OR patients being newly		

	diagnosed with AF and initiated on Pradaxa® or VKA.
Population:	Patients diagnosed with non-valvular atrial fibrillation (NVAF) and eligible for Pradaxa® or VKA treatment according to Pradaxa® or respective VKA label.
Variables:	
For objective 1:
 
Primary Outcome
 
For Cohort A (NVAF patients on VKA who are switched to Pradaxa®):
 
 - Mean PACT-Q2 scores at second and last assessment compared to baseline assessment. 
For Cohort B (newly diagnosed NVAF patients initiated to either VKA or Pradaxa®):
 
 - Mean PACT-Q2 scores at second and last assessment compared between treatment groups. 
Secondary outcome:
 
For Cohort A (switched to Pradaxa®):
 
 - Mean PACT-Q2 scores at last assessment compared to second assessment. 
For Cohort B (newly initiated to VKA or Pradaxa®):
 
 - Description of PACT-Q1 items at baseline. 
For objective 2:
 
Primary outcome:
 
Characterization of patients from both cohorts according to
 
 - Age - Gender - CHA2DS2-VASc score (R10-5332) - HAS-BLED score (modified HAS-BLED for newly initiated patients) (R10-6394) - Kidney function (creatinine clearance) - Co-morbidities - Co-medication - Dosing of Pradaxa - Duration of previous VKA treatment (for Cohort A)
Data sources:	- New data collection

	
- Questionnaires completed by patients- Patient characteristics completed by physician's judgement and records.
Study size:	1790 patients in 6 SEASK countries
Data analysis:	
In this non-interventional study, baseline and longitudinal follow-up data over 6 months will be collected for non-valvular AF patients with a current VKA therapy and subsequent initiation of Pradaxa® in Cohort A, and for newly diagnosed AF patients initiated on Pradaxa® or VKA in Cohort B. Data from baseline and the longitudinal follow-up will be summarized descriptively. For Cohort A, mean PACT-Q2 scores between assessments will be compared using paired t-tests. For Cohort B, mean PACT-Q2 scores between Pradaxa® and VKA patients will be compared using propensity score matched analysis.

Milestones:	
Planned start of data collection: 30 Apr 2016 Planned end of data collection: 11 Jan 2018 Planned final study report: 5 Jul 2018

5. AMENDMENTS AND UPDATES

None

6. MILESTONES

Milestone	Planned Date
IRB/IEC approval	20 April 2016
Start of data collection	30 April 2016
End of data collection	11 January 2018
Final report of study results:	05 July 2018

7. RATIONALE AND BACKGROUND

Pradaxa[®] (Dabigatran etexilate) is a direct Thrombin inhibitor approved in Europe, USA and many other Asian countries worldwide for the prevention of stroke and systemic embolism in adult patients with non-valvular atrial fibrillation with one or more risk factors. Pradaxa[®] has been studied in the RELY study, one of the largest atrial fibrillation outcome studies (P13-05668). Over the course of one year, all anticoagulated patients without outcome events (e.g. strokes or major bleedings) had stable HRQoL. There is a lack of data on how atrial fibrillation patients in Asia perceive Pradaxa[®] treatment in the context of anticoagulation management.

The decision in clinical practice to use Pradaxa[®] as the first novel anticoagulant or established vitamin K antagonists depends on many factors related to:

- a) The patient: Level of information, health status, comorbid conditions and demographic factors, perception of anticoagulant treatment, understanding of the burden of the disease, access to the medication, educational measures informing about medications and reimbursement status in a particular country.
- b) The treating physician: Stroke risk assessment, bleeding risk assessment, understanding and adherence to guidelines, access and use of medical education, interaction with patients and overall local health care system.

It is assumed that these factors in real world clinical practice vary e.g. between countries with different health care systems, between patients who start anticoagulation treatment versus those who have anticoagulation experience already or between the treatment initiation versus the mid-term follow up on Pradaxa[®] or vitamin K antagonists.

It is the aim of this non-interventional study to describe the patient perception of anticoagulation when treated with Pradaxa[®] to prevent stroke and systemic embolism while suffering from non-valvular atrial fibrillation (according to its approved indication in the approved dosages of 110 mg or 150 mg twice daily). To evaluate patient understanding of treatment and patient values it is important to assess patient's perception of the treatment in the context of overall disease management as close as possible to the clinical practice. Furthermore it is important to anchor the Pradaxa[®] treatment perception data in different ways, in order to determine on how previously and newly diagnosed NVAf patients perceive treatment with Pradaxa[®], in comparison to vitamin K antagonist treatment (being considered the standard anticoagulation treatment for stroke prevention in non-valvular atrial fibrillation over decades):

- Compare the treatment perception data of patients, who are switched to Pradaxa[®] treatment, to their perception about their previous anticoagulation (VKA) therapy, and
- Compare the treatment perception data of patients who are newly initiated Pradaxa[®] treatment to the treatment perception data of patients who are newly initiated to VKA treatment

These real world data are needed to guide the scientific community in designing educational efforts for doctors and their patients and to assess the potential values of patient adherence programs when using Pradaxa[®] as the first novel anticoagulant. Also such data, describing patient's perception on Pradaxa[®] anticoagulation in the context of

patient-physician interaction managing stroke prevention in atrial fibrillation cannot be obtained by market research.

8. RESEARCH QUESTION AND OBJECTIVES

8.1 RESEARCH QUESTIONS

This non-interventional study will address the following questions:

- How do patients with non-valvular atrial fibrillation perceive anticoagulation treatment for stroke prevention (stratified in cohorts of patients switched from previous treatment to Pradaxa[®], newly initiated treatment with Pradaxa[®], newly initiated treatment with VKA)?
-
- What are the characteristics of patients receiving anticoagulation treatment for stroke prevention regarding demographics, physician rated risk scores, kidney function, concomitant diseases and concomitant medications, treatment for SPAF (choice of treatment, dosing)?

Two cohorts of patients will be recruited:

Cohort A:

Patients having been treated with VKA and now being switched to Pradaxa[®]

Cohort B:

Patients newly diagnosed with non-valvular atrial fibrillation and initiated on either Pradaxa[®] or VKA.

8.2 OBJECTIVE

Primary objective

- Describe the atrial fibrillation patient's treatment perception by using the PACT-Q at three time-points at baseline, during initiation period and during the continuation period.

Secondary objective

- Characterization of patient population (incl. dosing) in the participating SEASK countries.

9. RESEARCH METHODS

9.1 STUDY DESIGN

This is a non-interventional multi-national, multi-centre study based on newly collected data.

The study will enrol consented patients with non-valvular atrial fibrillation (AF) in SEASK with a current VKA therapy and subsequent initiation of Pradaxa® (Cohort A) OR patients being newly diagnosed with AF and initiated on Pradaxa® or VKA (Cohort B).

Patients will be followed over an observation period of 6 months. Data will be collected at three time points:

1. At Baseline (initiation on Pradaxa® or VKA)
2. 30-45 days after initiation on Pradaxa® or VKA (initiation period)
3. 150-210 days after initiation on Pradaxa® or VKA (continuation period)

9.2 SETTING

It is planned that data of approximately 1790 patients will be collected from approximately 80 sites in 6 SEASK countries. Planned participating countries are Indonesia, Malaysia, Singapore, South Korea, Thailand and Vietnam.

9.2.1 Study sites

Cardiologists and non-cardiologist sites regularly prescribing Pradaxa® and VKA for stroke prevention in atrial fibrillation according to the respective country approved label will participate.

Selected sites within each country should include those physicians (e.g. cardiologists, non-cardiologists) and facilities (e.g. specialist offices, hospitals, outpatient care centres etc.) that reflect the clinical practice in that country. Investigators that are currently participating in the BI registry program 1160.129 (GLORIA) are not allowed to participate in this study.

These site selection criteria will help to ensure that the patients recruited into this study will represent the patients treated within that country. After initiation, every site should include the first consecutive suitable patients where decision for switch to Pradaxa® (Cohort A) or decision for initiation on Pradaxa® or VKA (Cohort B) has been made. In consecutive sampling, every eligible patient is selected until the required sample size is enrolled. This approach helps to reduce the likelihood of selection bias.

Balance between Cohorts within each country

Within each participating country, the recruitment of patients in Cohort A and Cohort B needs to be balanced (A:B = 1:2). Within Cohort B, the patient enrolment will be controlled as well, in order to ensure that an equal amount of data will be collected of AF patients newly treated with Pradaxa® (sub-Cohort B1) or with VKA (sub-Cohort B2)

(Pradaxa[®]:VKA = 1:1). Therefore, the sponsor may have to decide to close the enrolment of patients for one of the Cohorts (or sub-Cohorts) during the recruitment period, if the other (sub) Cohort is exceeding the maximum number of enrolled patients planned for that country/site.

The decision for therapy has to be taken prior to and independently of enrolment into the study. Only after the treatment decision for the patient is taken, the investigator can check and decide if a patient can be enrolled in Cohort A or Cohort B.

Patients will then have to sign informed consent before they can take part in the non- interventional study.

A log of all patients included into the study (i.e. having given informed consent) will be maintained in the ISF at the investigational site irrespective of whether they have been treated or not.

9.2.2 Study population

9.2.2.1 Inclusion Criteria

Cohort A:

- 1A. Written informed consent prior to participation
- 2A. Female and male patient's ≥ 18 years of age with a diagnosis of non-valvular atrial fibrillation.
- 3A. At least 3 months of continuous VKA treatment for stroke prevention prior to baseline assessment.
- 4A. Patients switched to Pradaxa[®] according approved country label and physician's discretion.

OR

Cohort B:

- 1B. Written informed consent prior to participation.
- 2B. Female and male patients ≥ 18 years of age newly diagnosed with non-valvular atrial fibrillation and no previous treatment for stroke prevention (no use of any OAC within one year prior to enrolment).
- 3B. Stroke prevention treatment initiated with Pradaxa[®] or VKA according to approved country label and physician's discretion.

Exclusion Criteria

1. Contraindication to the use of Pradaxa[®] or VKA as described in the approved country label

2. Patients receiving Pradaxa[®] or VKA for any other condition than stroke prevention in atrial fibrillation.
3. Current participation in any clinical trial of a drug or device
4. Current participation in a Registry, e.g. the Gloria registry program, on the use of oral anticoagulation in AF

9.2.2.2 Removal of patients from the study

Every patient has the right to withdraw consent at any time during the study, without the need for justification and without any impact on the routine therapy.

A patient is considered permanently discontinued or withdrawn from treatment if the patient did not complete the treatment with Pradaxa or VKA for the entire continuation period until Visit 3 and did not perform all visit 3 assessments.

Boehringer Ingelheim reserves the right to discontinue the study overall or at a particular study site at any time for the following reasons:

1. Failure to meet expected enrolment goals overall or at a particular study site.
2. Emergence of any efficacy/safety information that could significantly affect continuation of the study, or any other administrative reasons.
3. Violation of the protocol, or the contract by a study site or investigator, disturbing the appropriate conduct of the study.

In the framework of NIS study, the Investigators are responsible for treatment and may remove patients at any time according to his/her medical judgement.

The investigator / the study site will be reimbursed for reasonable expenses incurred in case of study termination (except in case of the third reason).

9.2.2.3 Visit schedule

Collection of patient data should be managed during routine practice visits. The time-schedule below can only be a recommendation; if a patient does not visit the site at these time points, data will not be collected (no visits will be conducted solely for study purposes).

Visits must be performed face-to-face and cannot be performed by phone, email or fax, as the patient has to complete the self-administered questionnaires.

1. At Baseline (at initiation on Pradaxa[®] or VKA)
2. 30-45 days after initiation on Pradaxa[®] or VKA (initiation period)

3. 150-210 days after initiation on Pradaxa® or VKA (continuation period)

Table 9.2.2.3: 1 Flow Chart / Schedule of Data Collection

Visit	1	2	3
Assessment	Baseline	Initiation period	Continuation period
Day	1	30-45 days	150 – 210 days
Informed Consent ¹	X		
Patient demographics: age, gender	X		
Concomitant diseases / co-morbidities	X	X	X
Concomitant therapies	X	X	X
Healthcare system characteristics ²	X		
HAS- BLED score (to be calculated in the eCRF)	X		
CHA ₂ DS ₂ -VASc score (to be calculated in the eCRF)	X		
Inclusion/exclusion criteria	X		
Duration of previous VKA treatment (for Cohort A)	X		
Reasons for switch to Pradaxa® (for Cohort A)	X		
Start Pradaxa® or VKA	X		
Pradaxa® dosing (110 or 150 mg) and reasons for dose changes	X	X	X
Creatinine clearance calculation ³	X	X	X
Weight ⁴	X	X ⁴	X ⁴
ADR (serious and non-serious), fatal AE, pregnancy collection		X	X
Reason for Pradaxa®/VKA discontinuation		X	X
PACT-Q1 questionnaire	X (for Cohort B only)		
PACT-Q2 questionnaire	X (for Cohort A only)	X (both Cohorts)	X (both Cohorts)

Footnotes:

1. Written Informed Consent must be obtained prior to the baseline visit assessments.
2. The type of hospital/practice and speciality of treating physician must be entered
3. Creatinine clearance can only be calculated in the eCRF (via Cockcroft-Gault Formula) if serum creatinine value is available from already existing laboratory reports. No lab assessment must be performed for the study at the baseline Visit 1, Visit 2 and/or Visit 3. See also footnote 4.
4. Weight must be determined at Visit 1. At Visit 2 and/or 3, only if existing serum creatinine value is available at Visit 2 and/or 3.

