9.2.3 Study visits

Baseline visit:

No data collection for study purposes must be performed unless the patient has consented to participate in the study. Once the patient has signed the informed consent form, the patient is considered to be enrolled in the study and patient details should be recorded on the enrolment log.

The following procedures will be performed at the baseline visit:

- Sign informed consent form
- Review of inclusion and exclusion criteria
- Collection of demographic data: age, gender,
- Collection of concomitant diseases/co-morbidities in the medical history and at baseline
- Collection of current concomitant therapies
- Weight
- Creatinine Clearance: serum creatinine value (if available) to be entered on eCRF, Creatinine Clearance according to Cockcroft-Gault formula to be automatically calculated CHA2DS2-VASc and HAS-BLED score calculation in eCRF
- For Cohort A only: duration of previous treatment with VKA to be documented
- For Cohort A only: reasons for switch to Pradaxa[®] to be documented
- Documentation of Pradaxa[®] dosing
- Patient will be asked to complete the following patient related questionnaires:
 - PACT-Q2 (Cohort A only)
 - PACT-Q1 (Cohort B only)
- Treatment with Pradaxa[®] or VKA will be initiated

Initiation period:

During a routine practice visit occurring at 30 – 45 days after initiation of treatment, the following assessments will be documented:

- Current dosing of Pradaxa[®] and reasons for dose change (if applicable)
- New or changed concomitant diseases/co-morbidities
- Changes in concomitant therapies
- Creatinine Clearance: serum creatinine value (if available) to be entered on eCRF, Creatinine Clearance according to Cockcroft-Gault formula to be automatically calculated
- Weight (if needed for creatinine clearance calculation at V2)
- Collection and reporting of ADR (serious and non-serious), fatal AEs, or pregnancies (if applicable)
- Reasons for Pradaxa[®] or VKA discontinuation (if applicable)
- Patients will be asked to complete the PACT-Q2 questionnaire

Continuation period:

During a routine practice visit occurring at 150-210 days after initiation of treatment, the following assessments will be documented:

- Current dosing of Pradaxa[®] and reasons for dose change (if applicable)
- New or changed concomitant diseases/co-morbidities
- Changes in concomitant therapies

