11.2 ADVERSE EVENT AND SERIOUS ADVERSE EVENT COLLECTION AND REPORTING

The investigator shall maintain and keep detailed records of all AEs in their patient files.

Collection of AEs

The study design is of non-interventional nature and the study is conducted within the conditions of the approved marketing authorisation. Sufficient data from controlled interventional trials are available to support the evidence on the safety and efficacy of the studied BI drug. For this reason the following AE collection and reporting requirements have been defined.

The following must be collected by the investigator in the (e)CRF from signing the informed consent onwards until the end of the study:

- all adverse drug reaction (ADRs) (serious and non-serious),
- all AEs with fatal outcome,
- all pregnancies

Note: For all patients on Pradaxa[®] these data must be recorded on the AE pages in the eCRF. The separate NIS AE form or Pregnancy Monitoring Form must be used for Pradaxa[®] patient only (see 'Expedited Reporting' below).

All ADRs, including those persisting after study completion must be followed up until they are resolved, have been sufficiently characterized, or no further information can be obtained.

The investigator carefully assesses whether an AE constitutes an ADR using the information below.

Causal relationship of adverse event

The definition of an adverse reaction implies at least a reasonable possibility of a causal relationship between a suspected medicinal product and an adverse event. An adverse reaction, in contrast to an adverse event, is characterised by the fact that a causal relationship between a medicinal product and an occurrence is suspected.

Medical judgment should be used to determine the relationship, considering all relevant factors, including pattern of reaction, temporal relationship, de-challenge or re-challenge, confounding factors such as concomitant medication, concomitant diseases and relevant history.

Arguments that may suggest a **reasonable causal relationship** could be:

- The event is **consistent with the known pharmacology** of the drug
- The event is known to be caused by or **attributed to the drug class**.
- A **plausible time to onset of the event** relative to the time of drug exposure.
- Evidence that the **event is reproducible** when the drug is re-introduced
- **No medically sound alternative etiologies** that could explain the event (e.g. preexisting or concomitant diseases, or co-medications).

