7.9 SAFETY ANALYSIS

Safety analyses will be performed separately for Cohort A and B and by treatment for Cohort B, and will include all eligible patients. Statistical analysis and reporting of safety parameters will be descriptive in nature; and will be based on BI standards. No hypothesis testing is planned.

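### The visit rule makes no exception for safety data, which conflicts with protocol 11.2, and nothing tells sites how to find ADRs or deaths in patients who do not return

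*Protocol*

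**What the plan says.** Protocol 9.2.2.3 presents the visit times as a recommendation, then adds that "if a patient does not visit the site at these time points, data will not be collected", with a remark that no visit is to be made just for the study. It continues: "Visits must be performed face-to-face and cannot be performed by phone, email or fax, as the patient has to complete the self-administered questionnaires". In the flow chart of that section the row "ADR (serious and non-serious), fatal AE, pregnancy collection" is marked at Visits 2 and 3 and nowhere else. The row for the reason for discontinuing Pradaxa or VKA is marked in the same way. Section 9.2.3 repeats both items in its lists for the 30-45 day and 150-210 day visits.

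Protocol 11.2 sets a different scope. ADRs, "all AEs with fatal outcome" and pregnancies "must be collected by the investigator in the (e)CRF from signing the informed consent onwards until the end of the study". This duty is not tied to visits and covers both treatments. For Pradaxa patients a separate NIS AE form is added, due within 24 hours for serious ADRs and fatal AEs and within 7 calendar days for non-serious ADRs. The form is not required for VKA patients.

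On the analysis side, protocol 9.7.5 limits the safety analysis to enrolled patients for whom follow-up took place. SAP 7.9 analyses the cohorts separately "and will include all eligible patients", and SAP 6.3 defines eligible as having taken the prescribed treatment and having no important protocol violation. The SAP history table records this change. Both documents relate events to the number of patients treated and to person-years.

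**The concern.** A site that follows 9.2.2.3 to the letter enters nothing for a patient who does not come. A site that follows 11.2 enters whatever it learns. The difference matters because death, admission to hospital, or stopping the drug after a bleed are themselves reasons for not attending. A patient who has died cannot come to a face-to-face visit, so a fatal-AE slot governed by an attendance rule defeats its own purpose. The reason given for face-to-face visits, the self-completed questionnaire, does not apply to ADRs, vital status or the date and reason of stopping.

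At stake are the completeness of the ADR and death tables, and the account of why patients were lost, which protocol 9.7.6 and 9.9 and SAP 6.6 all promise.

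**Working it through.** **1. The two rules side by side.**

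| Question | Protocol 9.2.2.3 and 9.2.3 | Protocol 11.2 |
|---|---|---|
| When are events recorded? | At Visits 2 and 3 | Consent to end of study |
| Patient does not attend? | No data; safety not exempted | Duty unchanged |
| Fatal events? | A slot at an attended visit | All in scope |
| Second route? | None | Expedited form, Pradaxa only |
| Means of finding events in non-returners? | None | None |

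The first three rows conflict if both sections are applied literally. The last row is a gap in both.

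**2. Is the gap closed elsewhere?** Protocol 9.4 draws diseases, therapies and dosing from the physician's records but does not name ADRs or vital status. Protocol 9.10.4.1 lists ADRs, fatal AEs and the end of participation as source data, without saying how they are obtained when the patient stays away. Under protocol 9.8, unreported safety events are looked for in entered eCRF data and completed questionnaires, and no regular source verification is planned; a patient with no visit may have neither to review. Protocol 9.9 promises efforts to limit loss and to evaluate its reason and timing, but describes no step. No vital-status check, record look-up or contact procedure appears anywhere.

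**3. Effect on a percentage.** Let f be the share of eligible patients with no post-baseline safety information, p the event proportion in the others, and r the ratio of event risk in the first group to that in the second. If no event in the first group is recorded:

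- true proportion = (1 - f)p + f·r·p
- reported proportion = (1 - f)p
- reported / true = (1 - f) / [(1 - f) + f·r]

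With r = 1 this equals 1 - f. With r above 1, as when events cause the non-return, it is lower.

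**4. What the documents say about f.** They give only attrition allowances from protocol 9.5, set for the PACT-Q2 comparisons.

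- Cohort A: 598 × 0.80 = 478 patients; at a standardized difference of 0.13 a paired t-test has power 0.81, in line with the stated figure of over 80%. Allowance: 598 × 0.20 = 119.6, about 120 patients.
- Cohort B: 1192 × 0.70 / 2 = 417 pairs; at 0.14 the power is 0.81, again as stated. Allowance: 1192 × 0.30 = 357.6, so at most about 358 patients, because matching loss is included and not split out.

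Neither number is f. A patient lost after Visit 2 already has a post-baseline record, and some events in lost patients will be reported under 11.2. For Cohort A, if f lies anywhere from 0 to 0.20 and r = 1, reported / true lies between 1.00 and 0.80. That is a range under assumptions, not an estimate. For Cohort B the allowance cannot be turned into a value of f. No event rates are given, so the number of missed events cannot be computed for either cohort.

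**5. Effect on person-year rates.** SAP 7.9.1 also uses observed time at risk. Here the effect depends on where a non-returner's time ends. SAP 7.8 counts exposure to the last administration and has a rule for death, but none for a patient whose last administration date is unknown because nothing was recorded after baseline.

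**6. Pradaxa against VKA in Cohort B.** The expedited form favours capture on Pradaxa. The more frequent contact with VKA patients, noted in protocol 9.9, favours capture on VKA. The two pull in opposite directions and the documents give nothing with which to weigh them.

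**The case against.** The strongest reply is that 11.2 is the dedicated adverse-event section and so governs adverse events. Its duty is event-driven, and a 24-hour deadline cannot wait for a visit months away. The sentence in 9.2.2.3 sits among rules on scheduled visits and can be read as covering visit data only. SAP 6.1 accepts Visit 2 data from day 7 to 124 and Visit 3 data from day 125 to 365, so missing the nominal window does not by itself remove a patient's data. SAP 7.6 says that discontinuation is recorded on the eCRF, and SAP 7.8 uses the date of death, so records for non-completers are expected. Safety is not a study objective, the study is not a PASS, and the tables are descriptive.

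Most of this stands, and it rules out several stronger readings:

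- A reader might infer that deaths and serious ADRs will be lost. That follows only where sites apply the visit rule to safety data.
- A reader might infer that telephone contact is barred. The protocol says that visits cannot be held that way; it does not stop a site from learning of an event by telephone.
- A reader might infer that reasons for discontinuation are lost. They are expected on the eCRF; what is missing is a way to obtain them from someone who does not return.
- A reader might infer that the wider safety population in the SAP is a mistake. It is a logged revision.

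What the reply does not supply is a sentence exempting safety data from 9.2.2.3, or a means of finding events in non-returners. A duty to record what is known does not tell the site how to come to know it.

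**Conclusion.** The conflict between protocol 9.2.2.3/9.2.3 and 11.2 is in the current text and must be reconciled. If the visit rule is applied to safety data, events in patients who die or do not return can be missed on either treatment. Because SAP 7.9 keeps all eligible patients, those with nothing after baseline count as event-free, and the ADR and death percentages may then be too low. This rests on two assumptions: that some sites read the rule that way, and that the affected patients stay in the denominator.

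The size is unknown. A reader might apply the 30% allowance to an assumed 10% ADR rate and report 10% × 0.70 = 7.0%. The documents do not support that: the 10% is not in them, and the 30% includes matching loss, which has no bearing on whether an ADR is recorded. Nor do they support a claim that either treatment is favoured.

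The primary PACT-Q2 comparisons do not depend on this point. It should still be corrected, because safety is a planned and reported analysis.

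**What to change.** **Protocol.** Reconcile 9.2.2.3 and 9.2.3 with 11.2:

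- Limit the attendance and face-to-face rule to the PACT-Q questionnaires.
- State that ADRs, fatal AEs, pregnancies, vital status, and the date and reason of stopping are entered from the physician's records or any routine contact, in the same way for both treatments.
- Require one record check at the end of the Visit 3 period for each enrolled patient without a Visit 3.

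**SAP 7.9.**

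- Report, by cohort and by treatment, the number of patients with no post-baseline safety information.
- Add a sensitivity table restricted to patients with actual follow-up, as in protocol 9.7.5. Define follow-up independently of whether an event was reported, for example as an attended Visit 2 or 3 or a completed record check. A set defined by having any safety report would let non-returners in only when they had an event, and would push the percentages up.
- End person-time at the last date with safety information.

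**Cost.** Wording in both documents and one chart look-up per patient without a Visit 3. No visit, procedure or laboratory test is added, so the non-interventional design is kept. The count of patients without safety information needs no new data.
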